 - CTCAE grade ≥ 3 interstitial lung disease or pneumonitis which cannot be attributed to another cause
 - CTCAE grade ≥ 3 nausea, vomiting or diarrhoea, despite optimal anti-emetic or anti-diarrhoeal therapy, and which cannot be attributed to another cause
- Any other CTCAE grade ≥ 3 toxicity which, in the opinion of the investigator, is clinically significant and related to the study drug, with the exception of sub-optimally treated nausea, vomiting or diarrhoea

The National Cancer Institute (NCI) CTCAE version 3.0 will be used whenever applicable to characterise DLTs. However, pre defined stopping criteria will supersede the CTCAE criteria.

If patients present with a potential DLT, the patient should be promptly investigated to define the aetiology of the symptoms. The use of appropriate (ie non restricted) medications in prophylactic or therapeutic management of toxicities are permitted. In the case of suspected interstitial lung disease, specialist pulmonary consultation is strongly recommended.

The decision to interrupt dosing or to stop a patient from receiving further dosing will be taken by the principal investigator, in consultation with the study team, based on the clinical significance of the observed toxicity. If the toxicity is subsequently determined by the SMC to not be a DLT, this patient will be replaced.

The principal investigator, in consultation with the study physician, may request replacement of patients who develop DLTs which are attributed to confounding factors and concomitant medications started during the DLT assessment period. Confounding medications for the specific DLT will be prohibited for the new patient(s) recruited to that dose group.

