3.4.5 Blinding and procedures for unblinding the study (Not applicable)

3.4.6 Concomitant medication

Patients are not eligible to enter the study if they have taken any of the following within the specified timeframe:

- Within 4 weeks prior to study entry: chemotherapy (within 6 weeks for nitrosurea or mitomycin C), radiotherapy, hormone therapy (except for androgen-deprivation therapy for patients with prostate cancer), immunotherapy and any other anti-cancer therapies
- Currently receiving, or taken within 7 half-lives of the drug: drugs (eg, prescribed and non-prescription) with known significant CYP3A4 and CYP2D6 inhibitor and inducer effects (see [Appendix F](#) for details). Where drug half-life information is not available, the patient should not have received the therapy within the last 4 weeks
- Currently receiving, or taken within 7 half-lives of the drug: drugs designated as Class I Arizona risk for QT prolongation (see [Appendix F](#) for details). Agents designated as Class II Arizona risk for QT are allowed provided the patient has received these agents for at least 5 half-lives of the drug with no change in dose
- Currently receiving anti-seizure medication.

Ongoing treatment with anti-cholinergic medication, oral steroids, angiotensin converting enzyme (ACE) inhibitors, potassium-sparing diuretics or potassium supplements is allowed, provided the patient has been on therapy for at least 4 weeks with no changes in dose in that time.

All medications and aspects of medical management that are standard in the treatment of advanced solid malignancies, as well as any treatment for inter-current diseases, will be allowed during the treatment period, with the exception of the following:

- Concomitant anti-cancer agents or any other investigational agents
- Agents designated as Class I Arizona risk for QT prolongation (refer to [Appendix F](#)). If agents designated as Class II Arizona risk for QT prolongation are started during the DLT assessment period, they may influence the QT interval (refer to [Appendix F](#))
- Drugs with known significant CYP3A4 and CYP2D6 inducer/inhibitory effects (refer to [Appendix F](#))
- Systemic steroids. (Systemic steroids may be administered at the discretion of the investigator).

Patients who receive any of the above concomitant medications during the period of DLT assessment (up to Day R21) could be considered non-evaluable and may be replaced.

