6.4.3 Description of analysis sets

Three patient analysis sets will be used as defined in Table 4; the safety set, the dose escalation evaluable set and the PK evaluable set. The primary analysis set will be the dose escalation evaluable set.

Table 4 **Definition of analysis sets**

Analysis set	Definition
Safety set	This population comprises all patients entered into the study who received at least one dose of AZD8931
Dose escalation evaluable set*	All patients in the safety set who have either experienced a DLT, or received at least 80% of planned doses of AZD8931 and who had all safety assessments completed during the DLT evaluation period
PK evaluable set	All patients in the safety set who have Day D1 PK data and/or have Day R14 PK data (and have received all doses during the day before Day R14)

*The SMC decide evaluability in the absence of appropriate assessments

Rules for identification of significant protocol violations will be given in the SAP. If a substantial number of patients are deemed to be protocol violators a separate ‘per-protocol’ analysis set will be determined, prior to analysis, which will exclude these patients.

6.4.4 **Methods of statistical analyses**

6.4.4.1 **Pharmacokinetic data**

The PK analysis is described in Section 6.1.1. The PK endpoints will be listed for individual subjects and summarised by dose level.

6.4.5 **Determination of sample size**

No formal sample size calculations were performed since the study follows a 3+3 dose group dose escalation design (see Section 3.1.2).

6.5 **Interim analyses (Not applicable)**

No interim analyses are planned.

6.6 **Data monitoring committee**

Working rules of the SMC are described in the SMC charter.

The SMC will comprise:

- The principal investigators of all sites
- The AstraZeneca physician
- The Medical Monitor.

In each case at least one deputy may be nominated.

On a case-by-case basis, the SMC may seek advice from further experts, including qualified representatives of AstraZeneca/

Following completion of the DLT period by ≥ 3 evaluable patients, the SMC will review all available data and decide upon dose progression. Further ‘ad-hoc’ meetings of the SMC may be convened, if required.

The safety review of data from each dose group will lead to one of 4 possible outcomes:

- Escalate to a higher dose
- Repeat dose level in further patients to obtain 6 evaluable patients at that dose level

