1. GUIDANCE TO INVESTIGATORS REGARDING OPTIMAL THERAPY OF RASH

Investigators are recommended to institute appropriate management of AZD8931 rash-related adverse events in line with published recommendations, established practices, and investigator discretion relating to the management of rash associated with EGFR inhibitors. The D0102C00002 study protocol allows for the use of appropriate measures and protocol permitted medications in prophylactic or therapeutic management of toxicities in the study.

Systemic and topical therapies at or before the occurrence of rash of CTCAE Grade 3 severity (according to Version 3 Common Terminology Criteria for Adverse Events) are recommended. Appropriate systemic therapy may include permitted antibiotics, antihistamines and anti-inflammatory agents. AZD8931 treatment should be temporarily suspended if the rash progresses to CTCAE grade 3 severity.

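### Section 3.4.6 gives systemic steroids conflicting statuses and makes their use a discretionary ground for replacement that Table 4 does not contain, so evaluability can be settled after the toxicity is known

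*Protocol*

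**What the plan says.** Section 3.4.6 first accepts patients on ongoing oral steroids at entry, "provided the patient has been on therapy for at least 4 weeks with no changes in dose in that time". It then says that standard treatments "will be allowed during the treatment period, with the exception of the following", and the fourth item on that list is: "Systemic steroids. (Systemic steroids may be administered at the discretion of the investigator". The sentence after the list reads: "Patients who receive any of the above concomitant medications during the period of DLT assessment (up to Day R21) could be considered non-evaluable" and adds that such patients may be replaced. It names no criterion, decision maker or timing, and makes no exception for a patient who has had a DLT.

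Table 4 in Section 6.4.3 defines the dose escalation evaluable set, which is also the primary analysis set, as "All patients in the safety set who have either experienced a DLT, or received at least 80% of planned doses of AZD8931", the second group also needing complete safety assessments. Medication plays no part. The footnote gives the SMC a say on evaluability only where assessments are missing.

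Three other places bear on this:
- Section 3.4.4 lists non-evaluability as a ground for replacement and refers to Section 6.4.3 for its meaning. It also allows replacement after a DLT attributed to confounding medication.
- Section 3.1.5 says that, once the study physician has been consulted, the principal investigator "may request replacement of patients who develop DLTs which are attributed to confounding factors and concomitant medications started during the DLT assessment period".
- Section 3.4.3 makes a dose-reduced patient non-evaluable, but expressly spares one who has already had a DLT.

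**The concern.** Dose decisions rest on counts of 0, 1 or at least 2 DLTs among 3 to 6 evaluable patients, so who is counted matters as much as what is observed. A steroid can be started because of a toxicity, and Section 3.4.6 then opens the question of whether that patient counts. Treatment is open-label, so the answer can be given with the event in view.

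Steroid status also touches the DLT definitions. Section 3.1.5 allows only non-restricted drugs for managing toxicity, and rash is a DLT only if it persists despite optimal treatment. Whether a systemic steroid is restricted cannot be read from Section 3.4.6. Section 3.2.2 itself names steroids as a possible confounder of post-prandial glucose, and confirmed fasting hyperglycemia is a DLT.

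At stake are the escalation decision, the MTD and the DLT rate reported for the primary analysis set.

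**Working it through.** **Step 1. The rules side by side.**

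| Patient | Table 4 | Section 3.4.6 | Section 3.1.5 attribution route |
|---|---|---|---|
| Has a DLT; steroid given afterwards to treat it | Evaluable, DLT counted | May be called non-evaluable and replaced | Does not apply: a drug given after onset did not cause the event |
| Has a DLT attributed to a steroid started in the period | Evaluable, DLT counted | May be replaced | Replacement may be requested |
| Toxicity below the DLT definition; steroid given; at least 80% of doses and all assessments | Evaluable, no DLT | May be replaced | Does not apply |
| Stable oral steroid since before entry; 80% of doses and assessments met; no DLT | Evaluable, no DLT | Accepted at entry, but the later bullet does not separate old from new use | Does not apply |

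No section says which rule prevails.

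**Step 2. Size of the possible effect.** The protocol gives no target DLT rate or operating characteristic, so there is no stated figure to reproduce. What follows is an illustration.

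Inputs from the protocol: at least 2 patients with DLT make a dose non-tolerated, one DLT in a small cohort leads to expansion, and no DLT leads to escalation (Section 3.1.2). Fewer than 2 DLTs in 6 is acceptable (Section 3.1.4).

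Assumptions: cohorts start with 3 patients; patients are independent with DLT risk p; f and g are the shares of DLT and non-DLT patients who are replaced; replacements carry the same risk p and the same replacement shares.

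Chance that a dose passes: P = (1−p)³ + 3p(1−p)⁵.

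At p = 0.33 with no selective replacement: 0.67³ + 3 × 0.33 × 0.67⁵ = 0.301 + 0.134 = 0.434.

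Effective DLT risk among counted patients: p′ = p(1−f) / [p(1−f) + (1−p)(1−g)].

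- f = 10%, g = 0: p′ = 0.297/0.967 = 0.307, P = 0.480.
- f = 25%, g = 0: p′ = 0.2475/0.9175 = 0.270, P = 0.557.
- f = 0, g = 25%: p′ = 0.33/0.8325 = 0.396, P = 0.315.
- f = g = 25%: p′ = 0.33, P = 0.434, no change.

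The pattern is the same at other risks. At p = 0.40, P goes from 0.309 to 0.351 (f = 10%) or 0.428 (f = 25%), and to 0.207 with g = 25%. If 6 patients are treated from the start, P = (1−p)⁶ + 6p(1−p)⁵, and at p = 0.33 it goes from 0.358 to 0.488 with f = 25%.

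**The case against.** The best defence is that Table 4 controls. A DLT alone makes a patient evaluable there, Section 3.4.4 refers to Section 6.4.3 for the meaning of non-evaluable, and Section 3.4.6 only says that recipients "could be considered non-evaluable and may be replaced". The steroid bullet can also be read as a default against use with room for medical need, since the same section later lets the investigator give any medication needed for safety. SMC decisions are by documented consensus, and the SMC charter is not available here.

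Much of this stands. It narrows the exposure of patients with a declared DLT. It does not close the gap: Section 3.4.6 creates a replacement ground that Table 4 lacks, neither yields to the other, and Section 3.4.3 shows that the protocol writes the DLT safeguard out when it wants it.

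Stronger readings that a reader might infer are not supported:
- *That the clause lowers the observed DLT rate.* The direction is open. Patients whom Table 4 leaves most exposed to Section 3.4.6 are those without a DLT, and replacing them overstates toxicity.
- *That steroids are the expected treatment for the toxicities under study.* The rash guidance in Appendix I says "Appropriate systemic therapy may include permitted antibiotics, antihistamines and anti-inflammatory agents". It does not name steroids, and the protocol gives no frequency of use.
- *That Section 3.1.5 lets a patient be replaced because a DLT was treated with a steroid.* It covers DLTs attributed to a medication or other confounder, not drugs given after onset.
- *That every 1-in-3 result could be turned into 0 in 3.* That would need every sole DLT patient to be replaced, against Table 4, by someone certain to have none. With one replacement at the same assumed risk of 0.33, the chance of passing is 0.301 + 0.444 × (0.67 + 0.33 × 0.301) = 0.643, and even that assumes every sole DLT patient is replaced.

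**Conclusion.** The conflict between stated rules is real and should be resolved. Systemic steroids are excepted, allowed and a possible ground for removal within a few lines, and the removal ground disagrees with the definition of the primary analysis set. The firmest instance is the steroid-treated patient whose toxicity does not meet the DLT definition, who has taken at least 80% of doses and has complete assessments: Table 4 counts that patient, while Section 3.4.6 allows replacement.

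Bias in the DLT count is possible, not shown. At an assumed DLT risk of 33%, the chance that a dose passes moves from 43% to 48–56% if 10% to 25% of DLT patients are replaced, and to 32% if only 25% of non-DLT patients are replaced. Replacement unrelated to outcome causes none. The risk and the replacement shares are assumptions, and the upward figures further require that Section 3.4.6 or the attribution route is used despite Table 4.

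**What to change.** Reconcile Section 3.4.6 with Table 4 and Sections 3.1.5 and 3.4.4:

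1. Give systemic steroids one status during the DLT period. Which status is the sponsor's clinical decision.
2. Add to Section 3.4.6 the safeguard already in Section 3.4.3, so that a patient who has experienced a DLT stays evaluable, except through the attribution route in Section 3.1.5.
3. State that a systemic steroid given to treat an event starting in the DLT period does not by itself make the patient non-evaluable or replaceable.

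A general rule that evaluability be judged without regard to DLT status would be the wrong repair. It would clash with Table 4 and allow a patient with a DLT who took a steroid for an unrelated reason to be dropped.

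The cost is a few sentences in Section 3.4.6 and matching cross-references, with no change to cohort size, assessments or data collection.

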3.4.7 Treatment compliance

When patients are at the clinic, compliance will be assured by supervised administration of AZD8931 by the investigator or his/her delegate.

When patients are not at the clinic, patients will be asked to return all unused study drug at each visit (if treatment is continuing). Compliance will be assessed by means of tablet counts of returned unused study drug at each clinic visit, and by monitoring of patient diary cards. Compliance will be calculated at the end of the study.

4. MEASUREMENT OF STUDY VARIABLES

The following study measurements will be obtained. The timing of these measurements is detailed in the study plan (Table 1). The following 'priority order' will be in effect when more than one assessment is required at a particular time point:

- AEs
- Echocardiography
- 12-lead ECG (recordings will start 5 minutes prior to PK sampling when triplicate recordings are acquired)
- Heart rate and BP
- Safety blood sampling

- PK sampling (planned for the exact time of assessment)
- Ophthalmological examination
- Dermatological examination
- Urine sampling.

NB: The order of assessments will not be explored in the data reporting.

4.1 Medical examination and demographic measurements

4.1.1 Enrolment medical examination and demographic measurements

The following screening and demographic data will be collected in the paper CRF (pCRF) in the 21 days prior to the first treatment visit (see [Table 1](#) for the timing of these assessments).

- Provision of written informed consent
 - Provision of written informed consent must be obtained at screening for all patients. Additional written informed consent for participation in the genotyping component and biomarker analysis is optional
- Date of birth, sex, height, weight and race
- Relevant medical and surgical history, including menstrual status, concurrent illness and recent and current medications
- Urine pregnancy test
- Previous anti-cancer therapy, including surgery (concomitant medications will be recorded from Screening until the Study Completion Visit)
- Echocardiography and ECG
- Chest X-ray
- Physical examination, including but not limited to the following body systems: general appearance, skin, head and neck, lymph node, thyroid, musculoskeletal/extremities, cardiovascular, lungs, abdomen, and neurological
- Safety blood sampling and urine sampling
- Dermatological examination (observational and symptom-directed)
- Ophthalmological examination (see Section [4.4.5](#))

- Vital signs (resting BP and heart rate, measured with the patient in a sitting position)
- Type of tumour, TNM (tumour, node, metastases) stage at diagnosis and at study entry, and ErbB2 status (if available)
- Tumour assessment according to local standards to define all areas of disease (eg, bone, liver and lung). Document measurable disease according to RECIST criteria (see [Appendix C](#)), using Computer tomography (CT) or magnetic resonance imaging (MRI) scan. The baseline tumour assessment must be within 4 weeks prior to the start of treatment. This does not need to be repeated prior to starting treatment unless the investigator believes that there has been a change in tumour burden. If imaging is repeated before study entry, the most recent assessment should be recorded as the screening assessment. For patients with prior first line chemotherapy the screening imaging tests must have been performed at least 4 weeks after the last cycle of prior chemotherapy.

For assessment of patient eligibility for study entry, blood samples for haematology (platelet count) and clinical chemistry analysis (total bilirubin, ALT, and AST) will be collected according to standard local practice and analysed at the local laboratory of each study centre using standard procedures. Confirmation that the values meet the inclusion or exclusion criteria must be recorded in the pCRF.

Histological or cytological confirmation of advanced solid malignancy is required for inclusion in the study.

Patients must fulfil all inclusion and exclusion criteria before being entered into the study and allocated to treatment.

4.1.2 Treatment period medical examinations

Refer to [Table 1](#) for details of examinations to be performed during the treatment period. Ophthalmological and dermatological assessments are detailed in Sections [4.4.4](#) and [4.4.5](#), respectively.

4.1.3 Medical examinations after completion of the DLT evaluation period

Refer to [Table 1](#) for details of examinations to be performed for patients who continue repeat dosing beyond the DLT evaluation period.

Patients who continue treatment with AZD8931 after the DLT evaluation period should have their safety parameters monitored and clinically assessed at least once during each cycle in accordance to the protocol schedule. From the second cycle onwards, periodic clinic visits are according to [Table 1](#). Where appropriate a visit window of ± 7 days is permitted for the scheduled study procedures to be combined.

4.1.4 Post-study medical examination

A post-study medical examination will be conducted approximately 7 days after last dose of AZD8931, as specified in [Table 1](#). Patients will be asked to contact their doctor (general practitioner) should they develop any eye symptoms in the 3 months after their post-study medical examination.

4.2 Pharmacokinetic measurements

For timing of individual samples refer to the study plan ([Table 1](#)).

4.2.1 Determination of drug concentration in biological samples

Analysis of plasma samples for the determination of AZD8931 will be the responsibility of the Clinical Pharmacology & DMPK Department, AstraZeneca, UK. If warranted, the samples may also be used for investigation/analysis of circulating metabolites and/or exploratory biomarkers.

4.2.2 Collection of biological samples

PK samples will be collected at the following time points for determination of AZD8931 plasma concentrations:

Days D1 and R14: pre-dose, 1, 2, 4, 6, 8, 12 (prior to AZD8931 administration on Day R14), 24 (D1 only), 48 (D1 only) and 72 (D1 only) hours post dose Days R3 and R7: pre-dose (see [Table 1](#)).

Depending on emerging data/information, the timings and number of PK samples may be altered, but the maximum blood volumes from scheduled samples given in [Table 3](#) will not be exceeded. The actual sample time and date of all PK samples must be recorded in the CRF.

All biological samples will be collected, processed, labelled and shipped to a central laboratory (), as per the laboratory study manual. At appropriate time intervals, the central holding laboratory will arrange to have the samples transported on dry ice to the appropriate laboratory(ies) for analysis. Samples should be analysed within the timeframe after collection for which the stability in the samples has been validated and found acceptable.

Samples will be disposed of after the Clinical Study Report has been finalised.

Venous blood samples (3 mL) for determination of AZD8931 in plasma will be taken at the timepoints detailed in the study plan (see [Table 1](#)).

4.3 Efficacy and pharmacodynamic measurement and variables

4.3.1 Pharmacodynamic/exploratory measurements

4.3.1.1 Plasma samples for measurement of biomarkers

Optional blood samples (3 mL) will be taken to include (but not limited to) markers of cell death, invasion and angiogenesis. For timing of individual samples refer to the study plan ([Table 1](#)).

All biological samples will be collected, processed, labelled and shipped to a central laboratory, as per the laboratory study manual.

The biomarkers planned to be measured will include (but not limited to) M30 and M65. Measurements of M30 and M65 are by ELISA and will be analysed at the . Samples may be analysed retrospectively. Any biomarker data generated may be reported separately and may also form part of a pooled analysis with other AZD8931 studies.

